## II. Data Collection Overview

The following table indicates the necessary case report forms to be completed at the given time point:

Form Name	Pre-op	Surgical & Immediate Post-Surgical	6 weeks	6 months	1 year	Years 2, 3, 4, 5 Post-Surgical
Informed Consent	X					
Inclusion/Exclusion Criteria	X					
Demographic Evaluation	X					
Operative Information		X				
Surgical Device Information		X				
Discharge Summary		X				
Physical Exam	X		X	X	X	X
FJS-12 (Forgotten Joint Score)			●	●	●	●
EQ-5D	●		●	●	●	●
KSS - Surgeon completed	X		X	X	X	X
KSS – Patient completed	●		●	●	●	●
Physician Assessment of Post-op Radiographs			X	X	X	X
Adverse Event Report		★	★	★	★	★
Protocol Deviations	★	★	★	★	★	★
Study Completion	★	★	★	★	★	★
Independent Radiographic Review			◆	◆	◆	◆

- X Completed by Investigator or Designee
- Completed by patient
- ★ Completed by Investigator or Designee as applicable
- ◆ Independent radiographic review may be performed by Sponsor’s designee, if applicable at discretion of Sponsor

The following table indicates the necessary case report forms required to be completed for revision patients:

FORM NAME	REVISION (as applicable)	COMMENTS
Physician Assessment of Post-op Radiographs	★	Mark the “pre-revision” exam period.
Adverse Event Report	★	Document adverse event resulting in the revision
Study Completion	★	Complete indicating “Study Prosthesis Removed” under Study Completion Status.

- ★ Completed by Investigator or designee as applicable

### III. Introduction and Purpose

Osteoarthritis (OA) is the most common type of arthritis causing considerable disability across broad populations. The economic burden of arthritis, specifically osteoarthritis is enormous with an estimated cost of \$60 billion in the United States and expected to increase to \$100 billion by 2020. The knee joint is the most common joint to develop OA and total knee arthroplasty (TKA) is the most frequently performed joint arthroplasty procedure for this condition. With an increase in the prevalence of arthritis, obesity, and old age, a further demand for TKA is projected to increase substantially over the next few years. In 2005, approximately 523,000 TKAs were performed nationally. The American Academy of Orthopedic Surgeons (AAOS) and Kurtz et al, have provided projections for future demand of TKA. In 2002, the AAOS had suggested an annual replacement load of 474,000 by the year 2030. In 2007, Kurtz et al, described an annual demand of 3.5 million by 2030. While these projections vary widely, both suggest a strong increase in demand for TKA, prompting significant interest from surgeons, healthcare institutions and orthopedic device manufacturers interested to better understand the future technological and economic burden of TKA.

Although, TKA has demonstrated effectiveness with substantive and sustained improvement in quality of life for individuals with moderate to severe osteoarthritis, functional performance in patients 1 year after TKA remains lower than for healthy adults, with reports of an 18% slower walking speed, 51% slower stair-climbing speed, and deficits of nearly 40% in quadriceps strength. Additionally, certain limitations in knee design systems require surgeons to accept compromises which can result in surgical inefficiencies and challenges in seizing desired outcomes. Patient expectations and an ever emerging population with active lifestyle also add a new requirement and need for innovative designs that bring advantages over traditional implants. Personalized implants with critical features of natural movement, contoured shape, and unique anatomic and physiologic composition can address these requirements. The current concepts in TKA warrant a personalized orthopedics initiative by offering a finer ability in identifying and precisely addressing the unique needs of patients. It is through this introduction of high fidelity implants, morphologic designs and intelligent instrumentation that each patient's knee can be distinctively and accurately reconstructed, allowing for clinical outcomes to be better optimized. Furthermore, such personalized systems will empower the surgeon to advance performance by providing a leading design that efficiently accommodates surgeons' intraoperative needs with minimizing surgical trade-offs and maximizing efficiency.

To address these clinical challenges and methodologically address new implant characteristics, a prospective, multi-center, longitudinal data collection model is being proposed. The objective of this study is to determine clinical performance/ outcomes and implant survivorship for commercially available *Persona*® fixed bearing implants used in primary total knee arthroplasty.

### IV. Study Objectives

The objective of this study is to obtain clinical performance (outcomes) data and survivorship for commercially available *Persona* fixed bearing knee components implanted in primary total knee arthroplasty. This will be done by analysis of validated outcome measurement tools, radiographs and adverse event data.

The assessments will include:

1. Implant survivorship based on removal of a study device
2. Safety based on incidence and frequency of adverse events
3. Clinical performance measured by overall pain and function, quality of life data, radiographic parameters and survivorship

## V. Study Design

This is a prospective, multicenter, non-controlled clinical study designed to facilitate the collection and evaluation of pain, function, quality of life, radiographic assessment, and adverse event data. A minimum of six U.S. sites will contribute to this study. Maximum enrollment per site will not exceed 100 implanted knees. Each Investigator will be skilled in total knee arthroplasty and experienced implanting the devices included in this study.

Each Principal Investigator will be responsible for obtaining Institutional Review Board (IRB) or Ethics Committee (EC) approval as required prior to conducting the study. In order to avoid potential selection bias, each Investigator will offer study participation to each consecutive patient presenting as a candidate for primary total knee arthroplasty using the commercially available (FDA cleared) *Persona* fixed bearing knee system. Candidates who express interest in study participation will be offered Informed Consent. All potential study subjects will be required to participate in the Informed Consent process and will not be considered enrolled in the study until the candidate has signed and dated the IRB/EC approved patient Informed Consent. Study data cannot be collected until the candidate has completed the informed consent process and signed and dated the IRB or EC approved Informed Consent.

All study subjects will undergo preoperative clinical evaluations prior to their total knee arthroplasty. The post-operative clinical and radiographic evaluations will be conducted at 6 weeks, 6 months, 1 year, 2, 3, 4, and 5 years.

The Investigator will review radiographs at each clinical evaluation interval to ensure radiographic evidence of adverse events is documented and reported to the IRB or EC and Sponsor as required. At Sponsor's discretion, Sponsor may request copies of these radiographs for independent radiologic review. Sponsor may request one central reviewer for all radiographs independent of the surgeon and institution.

## VI. Study Population

Study population for primary statistical analysis will be comprised of males and females who require primary total knee arthroplasty and satisfy the inclusion/exclusion criteria outlined in this section of the protocol. In order to avoid potential selection bias, each Investigator will offer study participation to each consecutive patient presenting as a candidate for primary total knee arthroplasty using the commercially available (FDA cleared) *Persona* fixed bearing knee system. Candidates who express interest in study participation will be offered Informed Consent.

#### A. Inclusion Criteria

1. Patient is 18 to 75 years of age, inclusive
2. Patient qualifies for a primary total knee arthroplasty based on physical exam and medical history, including diagnosis of severe knee pain and disability due to at least one of the following:
  - a. Rheumatoid arthritis, osteoarthritis, traumatic arthritis, polyarthritis
  - b. Collagen disorders and/or avascular necrosis of the femoral condyle
  - c. Post-traumatic loss of joint configuration, particularly when there is patellofemoral erosion, dysfunction or prior patellectomy
  - d. Moderate valgus, varus, or flexion deformities
  - e. The salvage of previously failed surgical attempts that did not include partial or total knee arthroplasty of the ipsilateral knee
3. Patient has participated in a study-related Informed Consent process
4. Patient is willing and able to provide written Informed Consent by signing and dating the IRB/EC approved Informed Consent form
5. Patient is willing and able to complete scheduled study procedures and follow-up evaluations
6. Independent of study participation, patient is a candidate for commercially available *Persona* fixed bearing knee components implanted in accordance with product labeling

#### B. Exclusion Criteria

1. Patient is currently participating in any other surgical intervention studies or pain management studies
2. Previous history of infection in the affected joint and/or other local/systemic infection that may affect the prosthetic joint
3. Insufficient bone stock on femoral or tibial surfaces
4. Skeletal immaturity
5. Neuropathic arthropathy
6. Osteoporosis or any loss of musculature or neuromuscular disease that compromises the affected limb
7. Stable, painless arthrodesis in a satisfactory functional position
8. Severe instability secondary to the absence of collateral ligament integrity
9. Rheumatoid arthritis *accompanied by* an ulcer of the skin or a history of recurrent breakdown of the skin
10. Patient has a known or suspected sensitivity or allergy to one or more of the implant materials
11. Patient is pregnant or considered a member of a protected population (e.g., prisoner, mentally incompetent, etc.)
12. Patient has previously received partial or total knee arthroplasty for the ipsilateral knee.

### VII. Study Device Information

*Persona* knee components included in this study are commercially available (FDA cleared) in fixed bearing left and right side configurations and various component sizes to accommodate anatomical variation. Fixed bearing components may be configured for use in posterior cruciate-retaining, cruciate-sacrificing, or cruciate-substituting knee arthroplasty procedures.

They are intended for long-term implantation in accordance with product labeling. Please refer to the package insert for additional information and instructions.

## VIII. Study Procedures

### A. Offer Study Participation

Study participation will be offered to each consecutive patient presenting as a potential candidate for primary total knee arthroplasty using the commercially available (FDA cleared) *Persona* fixed bearing knee system. Candidates who express interest in study participation will be offered Informed Consent. Prior to patient enrollment or any further patient evaluation for study eligibility, the patient must participate in the Informed Consent process and sign and date the IRB or EC approved Informed Consent.

### B. Informed Consent Process

For candidates that express interest, the Investigator or Designee will describe relevant study information, including the purpose, procedures, possible risks, and potential benefits associated with study participation. The Investigator or Designee will also review, along with the candidates, the Informed Consent approved by both the governing IRB or EC and the study Sponsor. Candidates shall have sufficient time to read and understand the IRB or EC approved Informed Consent and discuss whether they wish to participate in the study. Candidates will be asked to acknowledge whether all of their questions and concerns have been addressed to their satisfaction. Any questions that candidates may have will be addressed appropriately by the Investigator or Designee. Candidates will be further instructed that they are free to obtain additional information from the Investigator or Designee at any time, that they are free to decline participation, and that they are free to withdraw their consent and discontinue their participation at any time without prejudice.

After completing the Informed Consent process, candidates who agree to enter the study must sign and date the IRB or EC approved Informed Consent. The Informed Consent must be signed and dated prior to the date of the study surgery. For bilateral TKA candidates that agree to enroll for both operative sides, a separate Informed Consent must be signed and dated for each operative side.

A copy of the signed Informed Consent must be provided to the study subject. The original signed Informed Consent is to be filed in the subject's medical record, study subject binder, or regulatory binder.

Study data will not be collected until the Informed Consent has been signed and dated. If the candidate does not wish to participate (does not sign and date the Informed Consent), data for that candidate will not be collected for this study.

### C. Informed Consent Log

An Informed Consent Log (Appendix C) will be maintained at the site throughout the course of the study. The purpose of the Informed Consent Log is to provide documentation that all enrolled study subjects underwent the Informed Consent process, signed and dated the IRB or EC approved Informed Consent, and were provided with a copy of the fully executed

consent with all required signatures. All candidates who sign and date the approved Informed Consent for the study must be entered in the log. If a subject signs and dates additional Informed Consent(s) after enrollment (e.g., due to a protocol amendment, protocol revisions, etc.), subsequent signings will also be recorded in the log. The Informed Consent Log will be filed in the site Regulatory Binder for the study.

**D. Subject Enrollment**

Once the Informed Consent has been signed and dated by the subject, the subject will be considered enrolled in the study. A unique case identification number (Case ID) will be assigned to each participating subject/knee (bilateral subjects will be assigned a unique case ID number for each knee). This unique case ID number will be used throughout the study for identification. Case ID numbers will be assigned consecutively in ascending order per site, with the starting number for a given site defined by Sponsor.

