**H. Baseline/Pre-operative Assessment**

Baseline/pre-operative data will be collected on the following case report forms:

1. Inclusion/Exclusion Criteria
2. Demographic Evaluation
3. Physical Exam

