**B. Clinical Data Collection/Submission**

1. Summary of Case Report Form Data Collection  
Study data will be collected on study-specific Case Report Forms (CRFs) provided by Sponsor. For subjects having bilateral knee replacement, separate case report forms must be completed for each operative side.  
  
The following CRF guidelines should be followed:
  - Complete carefully and accurately.
  - Complete header information consistently across all case report forms for each individual study subject.
  - Use the study subject's initials in header section.
  - Use the study subject's unique Case ID number assigned as instructed.
  - Do not provide information that is not requested on the CRFs.
  - Ensure that all fields are completed. For fields completed by the subject, efforts should be made to obtain any missing responses prior to the subject completing their visit.
2. Data Submission  
Completed CRFs will be submitted directly to Sponsor by electronic data capture and submission via a method approved by Sponsor. Every effort must be made to ensure data submission to Sponsor is made within 30 days of the visit completion.
3. Quality Assurance of Data  
The Investigator should ensure the accuracy, completeness, legibility, and timeliness of the data reported to the Sponsor in the CRFs and in all required reports. Data reported on the CRF, which are derived from source documents, should be

consistent with the source documents or the discrepancies should be explained. All electronic systems used to create, modify, maintain, or transmit electronic study records will be validated according to 21 CFR Part 11(iii). Sponsor will maintain quality control systems, in accordance with Sponsor's policies and procedures.

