**A. General Statistical Methods**

Statistical methodology will consist of summarizing collected data descriptively. Categorical data (e.g., gender or race) will be summarized using counts and percentages, and 95% Confidence Interval (CI), over the time periods of interest. Continuous data, such as age, will be summarized by using means, medians, standard deviation, minimum, maximum, and 95% CI over the time periods of interest. Implant survival and return to function will be

summarized using a Kaplan-Meier method and presented with rates (as percentages) and confidence intervals.

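### Bilateral subjects are recorded once per knee, but Section XI.A neither counts person-level data once nor allows for two knees of one person in its confidence intervals (minor)

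*Combined protocol and SAP*

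**What the plan says.** The combined protocol and SAP sets the knee as the unit of record in three places.

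- Section VIII.B, for candidates who enrol both sides: "a separate Informed Consent must be signed and dated for each operative side".
- Section VIII.D: "bilateral subjects will be assigned a unique case ID number for each knee".
- Section IX.B.1: "For subjects having bilateral knee replacement, separate case report forms must be completed for each operative side".

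The eligibility criteria (Section VI.B) exclude earlier arthroplasty of the ipsilateral knee only, so a second knee may enter. The form lists in Sections II and VIII.H include the Demographic Evaluation and the EQ-5D, and neither list exempts them from the per-side rule. Site caps in the synopsis and Section V are counted in implanted knees.

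On analysis, Section XI.A opens with "Statistical methodology will consist of summarizing collected data descriptively". Gender and race are its examples of categorical data, to be given as counts and percentages with 95% intervals. For measurements it says "Continuous data, such as age, will be summarized by using means, medians, standard deviation, minimum, maximum, and 95% CI". Implant survival and return to function get Kaplan-Meier rates with intervals. The synopsis repeats this. Neither place names a unit of analysis for each outcome, a link between the two Case IDs of one person, or a variance method. Section XI.B names survivability as the primary endpoint.

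**The concern.** Section XI.A's own examples (gender, race, age) are facts about a person, while the data are collected per side. If the records are summarised as they arrive, each bilateral subject's demographics are counted twice, and so is the EQ-5D when one visit serves both knees. An ordinary interval treats the second copy as new information and comes out too narrow.

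Knee-level results (Knee Society Score, Forgotten Joint Score, radiographic findings, device removal) are properly counted per knee. Two knees of one person are nevertheless likely to be positively correlated, and an interval that assumes independence then understates the uncertainty. Section XI makes the descriptive summaries the basis of all study reports and allows their use in regulatory submissions and publications, so their error bars should be right.

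**Working it through.** **No plan figure to reproduce.** The documents give caps (15 sites × 100 knees = 1,500), a minimum of six sites, and 10% attrition. They give no bilateral share, within-person correlation, target survival or precision.

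**Assumed inputs.** b = share of persons with both knees enrolled (10, 20, 30%). ρ = correlation between the two records of one person: 1 for exact duplicates, 0.2-0.5 for knee scores, 0.05-0.1 for revision.

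**Formula.** N persons supply K = N(1+b) records, of which 2Nb belong to pairs. The paired share of records is s = 2b/(1+b) = 0.182/0.333/0.462. The variance of a mean or proportion over records is (σ²/K)(1 + sρ). An ordinary interval uses σ²/K, so:

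- the correct width is √(1 + sρ) times the ordinary width;
- the actual coverage of a nominal 95% interval is 2Φ(1.96/√(1 + sρ)) − 1.

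**Fully duplicated data (ρ = 1): demographics, and EQ-5D at a shared visit**

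| b | 1 + s | Coverage | Simulated coverage |
|---|---|---|---|
| 10% | 1.182 | 92.9% | 92.6% |
| 20% | 1.333 | 91.0% | 91.1% |
| 30% | 1.462 | 89.5% | 89.5% |

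The simulation used about 600 records and 20,000 runs. With one record per person, N = K/(1+b), and the interval is √(1+b) = 1.049/1.095/1.140 times as wide as the one from duplicated records. Simulated coverage returns to 94.7/95.0/95.1%.

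**Knee-level scores: extra width needed, √(1 + sρ) − 1**

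| b | ρ = 0.2 | ρ = 0.5 |
|---|---|---|
| 10% | 1.8% | 4.5% |
| 20% | 3.3% | 8.0% |
| 30% | 4.5% | 10.9% |

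**Survivorship.** At ρ = 0.05 the extra width is 0.5/0.8/1.2%; at ρ = 0.1 it is 0.9/1.7/2.3%. As an illustration, assume 600 knees, 3% revised and b = 20%. The ordinary half-width is 1.96 × √(0.03 × 0.97/600) = 1.365 percentage points. It becomes 1.365 × √1.017 = 1.376 at ρ = 0.05 and 1.365 × √1.033 = 1.388 at ρ = 0.1.

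A Kaplan-Meier simulation of this case (20,000 runs, 10% attrition of persons spread evenly over five years) gave a true standard error of 1.009 and 1.015 times the Greenwood value at correlations of about 0.06 and 0.11. With independent knees the ratio was 0.992; Monte Carlo error was about 0.5%.

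**The case against.** The strongest reply is that the plan leaves the unit open and does not choose the wrong one. Section VI describes the primary analysis population as males and females, and Sections VIII.E and VIII.J exclude subjects, so a statistician could count persons without departing from the text. The identifiers in Section IX (initials, date of birth, operative side) already allow linkage. The forms are not reproduced, so an instruction on a form cannot be ruled out. All of this is fair. But those population passages set no rule for analysis, and an instruction on a form would not supply a variance for paired knees.

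A reader might also infer more than the documents support:

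- **That coverage near 90% applies throughout.** It needs exact duplicates and b = 30%. After staged surgery, the two EQ-5D forms for a given interval fall on different dates and describe different recovery states. At ρ = 0.5 and b = 20%, coverage is 93.0%, against 91.0% for duplicates.
- **That double weight biases the means.** Bilateral persons would supply 18.2/33.3/46.2% of records, but that shifts a mean only if they differ from unilateral persons, and the documents give no such difference. It is a bias only if the target is the person; describing implanted knees is a legitimate choice.
- **That adverse-event percentages are distorted.** No passage requires a systemic event to be entered under both Case IDs or pairs a count of one unit with a denominator of the other. With both Case IDs counted over knees, there is no distortion when bilateral and unilateral persons have the same risk.
- **That the primary endpoint is compromised.** The knee is reasonably implied as the unit for device removal, and the effect on its interval is negligible.

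**Conclusion.** The gap is real and minor. Sections VIII.B, VIII.D and IX.B.1 create paired records, and Section XI.A provides neither a count-once rule nor a clustered variance. If the data are summarised as collected and any bilateral subjects enrol, intervals for demographics and shared-visit EQ-5D are too narrow, and those for knee-level scores are somewhat too narrow when the two knees are positively correlated.

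If b is 10-30%, the loss is about 2 to 5.5 points of coverage for exact duplicates (95 − 92.9 = 2.1; 95 − 89.5 = 5.5). Knee-score intervals need 1.8-10.9% more width, and survivorship intervals at most about 2.3%. Every one of these figures depends on the assumed b and ρ, and all are zero if b = 0. The study is single-arm and descriptive, with no hypothesis test, so the error bars are affected but no decision is.

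**What to change.** Add to Section XI.A, and mirror in the synopsis:

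1. Link the two Case IDs of a person, using the identifiers already held.
2. Summarise demographics once per person, with persons as the denominator.
3. For EQ-5D, use one record when both knees share a visit. Otherwise keep both records and use a person-clustered variance. One record per person after staged surgery would discard valid data.
4. Analyse device removal (Kaplan-Meier), Knee Society Score, Forgotten Joint Score and radiographic outcomes per knee, with a person-clustered variance (robust, jackknife or bootstrap).
5. For adverse events, use the same unit in numerator and denominator.
6. Report the numbers of both knees and persons.

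The cost is slightly wider intervals and a little extra analysis work. No new data are needed.
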